4.4.2.5 Adolescent Primary Care Traumatic Stress Screen (APCTSS)

The APCTSS¹⁹ is a 5-item measure of DSM-5 symptoms of PTSD. The participant is asked whether they have experienced each of the five symptoms within the past month, with a Yes/No response. Total scores range from 0-5, with a score of 2 or more being indicative of probably PTSD. A non-validated parent report version has been designed to be a direct comparison of the CYP self-report. Duration: 2 minutes.

4.4.2.6 Revised Child Anxiety and Depression Scale (RCADS)

The RCADS-25 ²⁰ is a 25-item measure used to assess symptoms of anxiety and depression in CYP. Each item is rated using a 4-point Likert scale (0= never; 3=always), with total scores ranging 0-45 on the anxiety subscale and 0-30 on the depression subscale. CYP self-report (RCADS-C-25) and parent-report (RCADS-P-25) versions will be administered. The parent-report measure has been adapted to include gender neutral language. Duration: 5 minutes.

4.4.2.7 Child Behaviour Checklist (CBCL), Youth Self-Report (YSR)

The CBCL ²¹ is an 113 item scale designed to measure behavioural and emotional functioning in CYP, across two broad dimensions, internalising and externalising problems. Each item is rated using a 3-point Likert scale (0= not true; 2= very true or often true). Parent-report questionnaires (CBCL) and Youth Self-Report (YSR) questionnaires will be obtained. Validated versions of the measures which include gender neutral language will be administered. Duration: 15 minutes.

4.4.2.8 Utrecht Gender Dysphoria Scale – Gender Spectrum (UGDS-GS)

The UGDS-GS ²² is an 18-item questionnaire that measures gender dysphoria i.e. distress relating from the incongruence between an individual's birth registered sex and their gender identity, and gender affirmation i.e. comfort from living in accordance with their gender identity. Respondents are asked to rate each item using a 5-point Likert scale (1= disagree completely; 5= agree completely). Total scores range from 0-90, with higher scores indicating higher gender related distress. Only CYP self-report versions will be obtained. Duration: 3 minutes.

4.4.2.9 Body Image Scale – Gender Spectrum (BIS-GS)

The BIS-GS ²³ is a gender neutral version of the Body Image Scale (BIS)²⁴ used to assess an individual's relationship with their body. The scale consists of 33 items. Respondents rate their feelings towards each body part using a 5-point Likert scale (1= very satisfied; 5= very dissatisfied). Respondents also rate whether they would want to change each body part if it was possible through medical or surgical treatment using a yes/no response. Each item includes a 'don't have' response if the individual does not have that body part (e.g. vagina). Respondents are then asked to rate how they feel about not having that body part using the same 5-point Likert scale, and to indicate whether they would want to change this. Higher scores indicate greater body dissatisfaction. Only CYP self-report versions will be obtained. Duration: 3 minutes.

4.4.2.10 Ask Suicide-Screening Questions (ASQ)

The ASQ is a brief 4-item instrument used to assess risk of suicide ²⁵; including suicidal ideation, history of suicide attempt and burdensomeness factors. Each item is answered using a "yes" or "no" response, with total scores ranging from 0 to 4. A non-validated parent report version has been designed to be a direct comparison of the CYP self-report. We will administer CYP self-report and parent-report versions at baseline and follow-up. The wording of question 4 will be altered at follow-up to assess whether the CYP has attempted suicide in the past year (i.e. since the previous time-point of data collection). Duration: 1 minute.

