4.4.3 Annual follow-up timepoints only

4.4.3.1 Annual health update

A questionnaire was designed to assess the CYP's current height and weight, current prescribed medications and diagnoses including neurodevelopmental, mental health and physical health, received in the past year. The questionnaire also assesses the number of GP appointments, planned surgeries or procedures, A&E attendances, or other unplanned admissions in the past year. The reasons for the GP appointments and A&E attendances will be elicited. The length of hospital admission for planned surgeries or procedures and admissions following an A&E attendance will also be measured. At follow-up, parents/carers/legal guardians of CYP under 16 will be sent this questionnaire and asked to complete it with their CYP. Self-report questionnaires will only be obtained from young people aged 16 and above. Duration: 6 minutes.

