4.5 Safety data

4.5.1 Adverse events

The measures included at each assessment point (domain 7 – adverse events) will assess several adverse events (AE) experienced by the CYP since the last assessment. For this study, these will include suicidal thoughts and behaviour (captured by the ASQ), a marked increase in the severity of anxiety or depression symptoms (captured by the RCADS), A&E attendances due to mental health, and any unplanned hospital admissions (captured by the Annual Health Update). Mental distress requiring unplanned hospital admission (captured by the annual health update as any mental health related A&E admission) will be recorded as a serious adverse event (SAE) and will be reported to the CYP's lead clinician or care coordinator at the CYPGS, or their GP. The total duration of hospital admission will be recorded.

4.6 *Ongoing*

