8. STATISTICAL METHODS

8.1 **PRIMARY OUTCOME**

The primary outcome for the PATHWAYS-HORIZON study is the mental health status and wellbeing of children referred to national gender services for young people in the UK. This will be measured using the CYP self-report version of the KIDSCREEN-10 ²³ questionnaire, which evaluates quality of life across ten dimensions.

8.2 **SECONDARY OUTCOMES**

Secondary outcomes can be split into smaller subcategories. All outcomes are marked as to whether they are continuous, binary, time-to-event or will only be displayed descriptively. Scales of gender-related distress, mental health symptoms and physical health measures:

- Utrecht Gender Dysphoria Scale Gender Spectrum (UGDS-GS), continuous
- Revised Children's Anxiety and Depression Scale (RCADS), continuous
- Body Image Scale Gender Spectrum (BIS-GS), continuous
- Parental Attitudes of Gender Expansiveness Scale for Youth (PAGES), continuous
- SCOFF questionnaire, binary
- Sexual attraction questionnaire, descriptive only
- Adolescent Primary Care Traumatic Stress Screen (APCTSS), continuous
- Romantic Relations questionnaire, descriptive only
- Gender identity question, descriptive only
- Height (cm) and weight (kg) as BMI, descriptive only
- Physical health diagnoses, descriptive only
- Parental 'about yourself' questionnaire, descriptive only

Scales of suicidal ideation, hospitalizations, mood symptoms, behavioural and functional difficulties, quality of life ratings

- Ask Suicide-screening Questions (ASQ) for suicidal ideation and behaviour, binary
- Child Behaviour Checklist (CBCL), continuous
- Youth Self-Report (YSR) for behavioural and emotional problems, continuous
- KIDSCREEN-52 for quality of life, all 10 domains continuous
- Difficulties in Emotion Regulation Scale 18 (DERS-18), for young people, DERS-29 for parents, continuous
- Hospitalisations of participants, binary
- Social transition questionnaire, descriptive only

Experiences of therapeutic options

- Rates of referral to, uptake of and completion of:
- Psychological therapy, binary
- Occupational therapy, binary
- Speech and language therapy, binary
- Clinical nursing, binary
- Youth work support, binary
- School/College support, binary
- Non-endocrine pharmacological treatments, binary

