8.4.2.2 BINARY OUTCOMES

For binary outcomes, a similar method as used in the primary outcome analysis will be used. A mixed-effects logistic regression will be used in place of the mixed linear model.

The fixed effects and random effects will be the same as those used in the primary analysis.

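### ASQ item 4 narrows from any past attempt at baseline to the past year at follow-up, so a binary ASQ outcome that includes it is biased towards apparent improvement from baseline

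*Protocol*

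**What the plan says.** Protocol section 4.4.2.10 describes the four yes/no items of the ASQ as "including suicidal ideation, history of suicide attempt and burdensomeness factors". On timing it says "We will administer CYP self-report and parent-report versions at baseline and follow-up", and Table 1 marks the ASQ at baseline, month 12, month 24 and each annual follow-up. The same section then changes one item: "The wording of question 4 will be altered at follow-up to assess whether the CYP has attempted suicide in the past year". A bracketed gloss there treats the past year as the interval since the preceding data collection.

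Section 8.2 lists the outcome as "Ask Suicide-screening Questions (ASQ) for suicidal ideation and behaviour, binary". Section 8.4.2.2 gives the model: "A mixed-effects logistic regression will be used in place of the mixed linear model", and adds "The fixed effects and random effects will be the same as those used in the primary analysis". Section 8.4.1 names timepoint first among those fixed effects.

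Two other sections bear on recall. The Annual Health Update (4.4.3.1) asks about "A&E attendances, or other unplanned admissions in the past year". Section 4.5.1 says the adverse-event measures pick up events "experienced by the CYP since the last assessment".

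**The concern.** The timepoint coefficient compares baseline with follow-up. For the ASQ the two ends of that comparison do not measure the same thing if item 4 is part of the outcome: baseline counts an attempt at any time, follow-up only a recent one. Someone whose sole positive answer is an older attempt leaves the numerator without any change in their state.

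The result would look like falling suicidality after entry to the service. It would also travel. Section 5.5 sends adverse events and outcome data by timepoint to the Data Monitoring Committee, and section 9.3 says selected HORIZON data give context for interpreting PATHWAYS TRIAL. Nothing in the protocol aligns the two wordings. Section 8.11 plans no sensitivity analyses, and the one mentioned in section 8.8 concerns missing data only.

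**Working it through.** **Inputs.** From the protocol: the item 4 wording (4.4.2.10), the timepoints (Table 1), the outcome type (8.2), the fixed effects (8.4.1, 8.4.2.2), a cohort of about 3600 (8.3) and the assessment windows (3.4.1). The protocol states no ASQ rate, so there is no figure to reproduce. The following are assumptions:

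- L, share who ever attempted: 5% to 30%
- r, share of those with an attempt in the past year: 0.25 to 1
- qn, chance of a yes on items 1 to 3 if never attempted: 0.2 to 0.4
- qo, the same chance if the only attempt is older than a year: 0.3 to 1

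**Direction.** Score one unchanged population under both wordings. A past-year attempt is also an attempt ever, so a person's score under the follow-up wording cannot exceed their score under the baseline wording. Any cut-off on a total that includes item 4 therefore gives an equal or lower proportion positive at follow-up, never a higher one.

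**Size, for an any-yes score.**

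- Baseline: b = L + (1 − L)·qn
- Follow-up: f = r·L + (1 − r)·L·qo + (1 − L)·qn
- Spurious fall: b − f = L·(1 − r)·(1 − qo)
- Marginal odds ratio: [f/(1 − f)] / [b/(1 − b)]

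| L | r | qn | qo | b | f | fall (points) | OR |
|---|---|---|---|---|---|---|---|
| 5% | 0.50 | 0.3 | 0.5 | 33.5% | 32.25% | 1.25 | 0.94 |
| 10% | 0.50 | 0.3 | 0.5 | 37.0% | 34.5% | 2.5 | 0.90 |
| 20% | 0.50 | 0.3 | 0.5 | 44.0% | 39.0% | 5.0 | 0.81 |
| 30% | 0.25 | 0.2 | 0.3 | 44.0% | 28.25% | 15.75 | 0.50 |
| 20% | 0.50 | 0.4 | 1.0 | 52.0% | 52.0% | 0 | 1.00 |

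With item 4 in the score, the fall is zero only when r = 1 (every ever-attempter also attempted in the past year) or qo = 1 (everyone with only an older attempt is positive on items 1 to 3).

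**Would it show?** A paired approximation is z = d / √[(2c + d − d²)/N], where d is the spurious fall and c the genuine change in each direction. I assume c of 5% to 10% and N of 1800 to 3600 pairs, that is 50% to 100% of the cohort.

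- d = 1 point: z about 0.9 to 1.8
- d = 3 points: z about 2.7 to 5.0
- d = 5 points: z about 4.3 to 7.8

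**Recall periods.** The window runs from 6 weeks (1.38 months) before to 5 months after the annual date.

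- Consecutive follow-ups: 12 ± (5 + 1.38), or about 5.6 to 18.4 months apart. A 12-month recall can overlap the previous period by up to 6.4 months or leave up to 6.4 months uncovered.
- After one missed wave (section 3.4.2 keeps such participants): 24 ± 6.38, or about 17.6 to 30.4 months. Subtracting 12 leaves about 5.6 to 18.4 months outside a 12-month recall.

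**The case against.** The strongest reply is that the protocol does not say how a 0 to 4 score becomes binary, and that outcome derivation is commonly left to the statistical analysis plan. If that plan uses items 1 to 3 only, the artefact disappears. This stands as a limit on certainty. A reader might infer that a fall in suicidality is bound to appear; the documents do not support that. The wording of section 8.2 points to item 4 being counted but does not settle it. The reply does not dispose of the point, however: a later plan can drop item 4, but it cannot recover a past-year attempt at baseline that was never asked about.

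Other objections hold in part:

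- An unlimited period at baseline is inferred. The protocol says history, not lifetime. Given the deliberate change at follow-up, no other reading is natural.
- Item 4 taken alone would give more striking figures (10% falling to 5% is an odds ratio of 0.47), but section 8.2 lists no item 4 outcome, so these do not describe a planned analysis.
- The planned model has a random participant intercept, so its odds ratio is conditional and would not equal the marginal figures above.
- The Annual Health Update is collected at follow-up only. It has no baseline shift and bears only on the recall point.
- The 5.6 and 18.4 month gaps are extremes. Section 3.4.1 schedules contact at 6 weeks before, on, and 2 weeks after the annual date.
- The ASQ is one of many secondary outcomes in an observational cohort.

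**Conclusion.** The point holds conditionally. If item 4 enters the binary ASQ outcome, the baseline-to-follow-up contrast is biased in one direction, towards apparent improvement. Contrasts among follow-up waves share the same wording and are unaffected. Under the assumed rates the spurious marginal odds ratio is roughly 0.5 to 0.9. It moves closer to 1 where older attempts are few, and is exactly 1 if item 4 is excluded or under either limiting condition in the working. An artefact of 3 points or more would probably reach nominal significance in this cohort; one of 1 point would not. These sizes are illustrative, because the protocol gives no rates.

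The secondary point rests on the protocol's own windows: a past-year period and a period since the last assessment are not the same. Sections 4.4.2.10, 4.4.3.1 and 4.5.1 treat them as though they were.

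**What to change.** State in the protocol or the statistical analysis plan which items form the longitudinal binary ASQ outcome, and choose one of two routes.

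1. Define it from items 1 to 3, whose wording is not stated to change. Report item 4 separately, as ever at baseline and since the last assessment at follow-up, with no baseline contrast. This needs no new data and can be settled at any time before analysis. The cost is that attempts leave the trended composite, so the outcome label in section 8.2 should change to match.
2. Add one yes/no item on past-year attempt at baseline, beside the existing item, and use it in the longitudinal outcome. The cost is one extra question. It cannot be filled in afterwards for participants who have already completed baseline.

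Reconcile the recall wording in sections 4.4.2.10, 4.4.3.1 and 4.5.1 by anchoring it to the date of last completion, which the ePRO could display. Under route 2 the trended item needs the same twelve-month period at every wave, so the anchored question would then be a separate one for adverse-event capture. Item 4 is yes/no and carries no count, so report it as a proportion alongside the interval length and not as an event rate.

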4.4.2.11 SCOFF Questionnaire

The SCOFF is a 5-item screening tool designed to identify the core symptoms of anorexia nervosa or bulimia nervosa²⁶. Each item is scored 0= "no" or 1= "yes". Total scores range from 0 to 5, with higher scores indicating more disordered eating behaviour and a score of 2 or more considered likely indicative of an eating disorder. A non-validated parent report version has been designed to be a direct comparison of the CYP self-report. CYP self-report and parent-report versions will be obtained. Duration: 1 minute.

4.4.2.12 Difficulties in Emotion Regulation Scale (DERS)

CYP will complete the short version of the Difficulties in Emotion Regulation Scale (DERS-18), which consists of 18 self-report items measuring emotional difficulties ²⁷. The DERS-18 generates scores across six subscales: nonacceptance of one's emotions, lack of goal-directed behaviour

during negative emotions, impulse control during negative emotions, emotional awareness, access to emotion regulation strategies and emotional clarity ²⁸. The 29-item DERS-P²⁹ will be administered to parents/caregivers. The DERS-P generates scores across four subscales: catastrophise, negative secondary, attuned and distracted. Each item is scored using a 5-point Likert scale (1= almost never; 5= almost always) such that higher scores indicate greater difficulties in emotion regulation. The parent measure has been adapted to include gender neutral language. Duration: 4 minutes.

4.4.2.13 Sexual Attraction

A questionnaire including one question 'Who are you attracted to?', with the response options, 'Prefer not to say', 'Males', 'Females', 'Males and females', 'Neither', 'Not sure' was designed to measure sexual attraction. Only self-report questionnaires will be obtained from young people aged 12 years and older. Duration: 1 minute.

4.4.2.14 Romantic Relations

Young people aged 12 and above will complete the ALSPAC Romantic Relations ³⁰ measure, which assesses whether young people have engaged in any of the 14 sexual behaviours from the Adolescent Sexual Activities Index (ASAI) ³¹, and the sex of the person with whom they did. Items are scored 0= they have not engaged in that sexual activitity, 1= they engaged in that sexual activity with the other sex, 2= they engaged in that sexual activity with both sexes, 3= they engaged in that sexual activity with the same-sex. Duration: 3 minutes.

4.4.2.15 Parental Attitudes of Gender Expansiveness Scale for Youth (PAGES)

The PAGES-Y³² is a 14-item self-report measure used to assess CYP's experience of parental acceptance of gender identity/ expression. The measure includes two subscales, perceived parental non-affirmation and perceived parental acceptance. CYP will rate each item based on their overall experience of support from both parents/caregivers within a single measure, as opposed to providing individual scores for each parent/caregiver. The PAGES-P³³ is a 16-item parent-report version measuring parental acceptance and support. Each item is responded to using a 5-point Likert scale (1= strongly disagree; 5= strongly agree), with higher overall scores indicative of greater perceived parental support. Duration: 3 minutes.

4.4.3 Annual follow-up timepoints only

4.4.3.1 Annual health update

A questionnaire was designed to assess the CYP's current height and weight, current prescribed medications and diagnoses including neurodevelopmental, mental health and physical health, received in the past year. The questionnaire also assesses the number of GP appointments, planned surgeries or procedures, A&E attendances, or other unplanned admissions in the past year. The reasons for the GP appointments and A&E attendances will be elicited. The length of hospital admission for planned surgeries or procedures and admissions following an A&E attendance will also be measured. At follow-up, parents/carers/legal guardians of CYP under 16 will be sent this questionnaire and asked to complete it with their CYP. Self-report questionnaires will only be obtained from young people aged 16 and above. Duration: 6 minutes.

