3.4.1 Assessment windows

Timing of annual assessments will be based on the date of the first assessment in the CYPGS. For all participants, the subsequent annual data collection windows will commence at 6 weeks prior to their annual date and will extend until 5 months after their annual date.

All participants will be contacted via text or email as preferred, 6 weeks prior to their annual date. Participants who do not respond will be contacted again on their annual date. A further reminder will be sent 2 weeks after their annual date for any participants who have not responded, at which point they will also be asked whether they can be contacted directly. If no response has been received after 3 reminders, a member of the research team will follow-up with the participant via phone to offer their assistance. At each point of contact participants will be given the option to withdraw from the study should they no longer wish to participate.

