3.4.2 Completion of assessments

Participants aged 12 years and older, and their parents/carers/legal guardians are expected to complete the assessments via an online survey platform (ePRO), as a starting point. For children under 12 years and CYP with neurodevelopmental conditions, such as autism, ADHD or intellectual disability, or specific learning disabilities such as dyslexia, those with English as a second language or due to personal preference, assessments may be conducted face-to-face, via video call, or through telephone interviews, depending on participant preference. This will also be offered to those where parents/carers/legal guardians have additional needs or English is not the first language. For these participant groups, where researchers are completing questionnaires directly with participants, they will be instructed to use their discretion in determining whether the informant understands the question and can provide valid responses.

All participants will be informed that a researcher can support them via telephone or video call to complete any assessments. Interpreters may be used as required. Researchers will proactively reach out to participants when the healthcare professionals or administrators in the CYPGS suggests this may be helpful, based on their clinical interactions and knowledge of the participants. These methods aim to support participation and accommodate specific needs. Participants missing a data collection window will be retained in the PATHWAYS HORIZON cohort for future data collection waves unless they withdraw, or the study ends.

4. Data Collection & Data Entry

Event/Form	Domain, information source (see legend)	Baseline	Month 12	Month 24	Annual Follow Up	Ongoing*	Estimated completion time (minutes)
Registration form & consent	R (1)	X					5
Eligibility	R (1)	X					10
Informed consent/ assent	SQ, PQ (1)	X					10
Medical history	D (6)	X					15
Demographic data	D (1)	X					2
ADHD (SNAP-IV)	PQ (5)	X					3
Autism (SCQ)	PQ (5)	X					5
Parental 'About Yourself' Questionnaire	PQ (3)	X					1
Status form	R (1)		X	X	X		1
Quality of Life (KIDSCREEN-52)	SQ, PQ (2)	X	X	X	X		7
Annual health update	SQ, PQ (6) (7)		X	X	X		6
Gender Identity Questionnaire	SQ (3), PQ**(3)	X	X	X	X		1
Social Transition Questionnaire	SQ (3)	X	X	X	X		1
Anxiety and depression symptoms (RCADS-25)	SQ, PQ (4) (7)	X	X	X	X		5
Suicide/ Self Harm (ASQ)	SQ, PQ (4) (7)	X	X	X	X		1
Gender dysphoria (UGDS-GS)	SQ (3)	X	X	X	X		3

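### The Annual Health Update asks about the past year, but the adverse events taken from it are counted since the last assessment, and the allowed timing lets the two periods differ by many months

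*Protocol*

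**What the plan says.** The Annual Health Update is completed at follow-up only. Protocol Section 4.4.3.1 says of it: "The questionnaire also assesses the number of GP appointments, planned surgeries or procedures, A&E attendances, or other unplanned admissions in the past year". The section also mentions reasons for GP and A&E visits and lengths of stay, but no event dates.

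Section 4.5.1 says that the adverse-event measures "will assess several adverse events (AE) experienced by the CYP since the last assessment", and names this form as the source for mental-health A&E attendances and unplanned admissions. Section 6 takes two of its four AE types, and its single SAE (unplanned mental-health admission), from the same form.

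On timing, Section 3.4.1 states: "Timing of annual assessments will be based on the date of the first assessment in the CYPGS". Follow-up windows "will commence at 6 weeks prior to their annual date and will extend until 5 months after their annual date". Section 3.4 lets a new case complete baseline up to five months after the first appointment. Sections 3.4.2 and 4.6.1 keep a participant who misses a wave in the cohort.

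Section 4.4.2.10 (ASQ, question 4 at follow-up) treats the past year and the time since the previous data collection as the same period.

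**The concern.** A fixed 12-month recall and a recall back to the last assessment are different questions unless forms fall exactly 12 months apart. The annual date is tied to the first clinic assessment, not to the previous form, and each form may be early or late, so the gap varies. If the gap exceeds 12 months, some time is covered by no form. If it is shorter, some time is covered by two. At the first follow-up, the recall can reach back before baseline.

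At stake are the AE and SAE counts that depend on this form, the reports to the clinician or GP and to the REC that follow from an SAE, and the safety tables sent to the DMC. An analysis plan cannot repair this. Without event dates, a duplicate cannot be recognised, an event before baseline cannot be moved, and an event that was never asked about cannot be recovered. Multiple imputation (Section 8.8) addresses missing outcomes, not a truncated recall on a completed form.

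**Working it through.** The plan states no figure to reproduce. The check is interval arithmetic on its windows.

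**Inputs**
- Recall period: 12 months (Section 4.4.3.1).
- Early limit: 6 weeks = 42 / 30.44 = 1.38 months. Late limit: 5 months (Section 3.4.1).
- Baseline: from about the first appointment to 5 months after it (Section 3.4).

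**Formulas.** For forms k waves apart, gap = 12k ± (5 + 1.38) = 12k ± 6.38 months. Unasked time = max(0, gap − 12). Time asked about twice = max(0, 12 − gap).

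| Interval | Gap (months) | Unasked | Covered beyond the interval |
|---|---|---|---|
| Consecutive follow-up forms | 5.6 to 18.4 | up to 6.4 | up to 6.4 (asked twice) |
| Baseline to Month 12, new cases | 5.6 to about 17.0 | up to about 5.0 | up to 6.4 (before baseline) |
| One missed wave between follow-up forms | 17.6 to 30.4, nominal 24 | 5.6 to 18.4, nominal 12 | none |

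**Month 12 worst case.** Baseline is at month 5 and the Month 12 form at 12 − 1.38 = 10.62. The gap is 10.62 − 5 = 5.62 months, so 12 − 5.62 = 6.38 months of recall lie before baseline. Of these, 5 months fall after the first clinic appointment and 1.38 before it. No Annual Health Update exists at baseline, so these events would be misattributed to follow-up, not counted twice.

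**Example.** After a missed wave, an admission 14 months before the next form lies outside that form's question, and no earlier form covered it if the last one was completed before the admission.

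**Typical size (illustration; completion dates are assumed).** With dates uniform over the window, a consecutive pair of follow-up forms leaves on average 1.06 months unasked and 1.06 months asked twice, and 71% of pairs are more than one month away from a 12-month gap. Over three waves (months 12, 24 and 36; 200,000 simulated participants; baseline at 0 to 5 months), the share of follow-up time never asked about with no missed waves is 7.9% for uniform completion and 4.4% for early-weighted completion. A separate early-weighted run gave 4.6%. If 20% of waves were missed the share would be about 16 to 19%, and if 30% were missed about 21 to 24%. The protocol gives neither rate.

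**The case against.** The strongest reply is that the form itself is not printed. Section 4.4.3.1 only describes it, and Section 4.4.2.10 suggests that the authors use the past year as shorthand for the time since the last assessment. This stands as a limit: events can be missed or misplaced, and it is not shown that they will be. It does not remove the conflict, because nothing in the protocol adapts the recall to the actual gap.

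A reader might infer more than the documents support:

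- **That the binary hospitalisation outcome is distorted.** For the mixed logistic model in Section 8.4.2.2, a fixed 12-month look-back gives every completed form equal exposure, which is an advantage. Section 8.2 also does not name that outcome's source. The mismatch bites on AEs and the SAE.
- **That all the excess look-back is double counting.** With no missed waves, it comes to about 6 to 10% of follow-up time, but true overlap between two forms is only about 4 to 6%. The rest precedes baseline.
- **That loss is selective because waves are missed around a crisis.** This is plausible, but nothing in the documents shows it.
- **That the DMC would be misled.** Section 5.5 says that AE and SAE capture is less comprehensive than in a randomised trial, that reports will make this clear, and that the DMC will not make recommendations from these data.

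Two further points stand in part. Section 3.4.1 concentrates contacts between 6 weeks before and 2 weeks after the annual date, followed by a phone call, so the lower end of 4 to 8% may be nearer the truth. And recall since the last form can reach 30.4 months after a missed wave, which will be less accurate than 12-month recall, though still better than not asking.

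**Conclusion.** The plan is inconsistent as written. Sections 4.4.3.1 and 4.5.1 set different periods for the same events, and Section 4.4.2.10 equates periods that the protocol's own timing rules allow to differ. The bounds follow from the protocol's windows alone: up to 6.4 months unasked or asked twice between consecutive follow-up forms, up to 6.4 pre-baseline months attributed to follow-up at Month 12, and about 12 months (5.6 to 18.4) unasked after one missed wave.

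The average loss of roughly 4 to 8% of follow-up time with no missed waves rests on assumed completion patterns. Anything larger rests on assumed missed-wave rates. Between consecutive follow-up forms, unasked and doubly covered time roughly balance on average under uniform completion, but that does not correct an individual SAE record. After a missed wave the error is loss only, so that is where safety capture is weakest. The conclusion covers AE and SAE capture. It does not show bias in the hospitalisation outcome or selective loss.

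**What to change.** Reconcile Sections 4.4.2.10, 4.4.3.1 and 4.5.1 on one recall period:

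1. Word the A&E and admission items as since the date of the last completed assessment, with the date pre-filled by ePRO (baseline for the first follow-up).
2. Record the month of each A&E attendance and admission, so that AEs and SAEs go to the right interval and duplicates can be removed.
3. Use the event month to keep a fixed 12-month definition for the binary hospitalisation outcome. Exposure then stays equal in the planned logistic model and no offset is needed. If baseline was less than 12 months before the first follow-up form, that form must still reach back 12 months, with the month keeping pre-baseline events out of the AE count. For new cases this affects only the first follow-up: by the earliest second form, at month 22.6, at least 22.6 − 5 = 17.6 months since baseline have been covered.

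The form was designed for this study, so no validated instrument is altered. The cost is one pre-filled date, one extra field per event, and longer recall after a missed wave. The change should be made before follow-up data accrue, because events not asked about cannot be recovered at analysis.
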